2.1 MULTIPLICITY ADJUSTMENT

A fixed sequence testing procedure (Westfall and Krishen 2001) will be used to control the overall type I error for the primary and the key secondary endpoints. The primary and key secondary endpoints will be tested in the order shown below at a two-sided 0.0496 significance level, proceeding sequentially starting from the primary endpoint and testing each after achieving statistical significance on the previous endpoint. The sequence for endpoint testing will be the primary endpoint, followed by key secondary endpoints in the following manner:

- 1. Proportion of patients with a ≥ 2-step improvement from baseline on the ETDRS-DRSS at Week 52
- 2. Rate of patients developing a vision-threatening complication (defined as PDR or ASNV) or CI-DME (defined as CST ≥ 325 µm) through Week 52
- 3. Rate of patients developing PDR or ASNV through Week 52
- 4. Rate of patients developing CI-DME (defined as CST ≥ 325 μm) through Week 52
- 5. Rate of patients developing ≥ 2-step worsening from baseline on the ETDRS-DRSS through Week 52
- 6. Proportion of patients with ≥ 3-step improvement from baseline on the ETDRS-DRSS at Week 52
- 7. Rate of patients developing ≥ 3-step worsening from baseline on the ETDRS-DRSS through Week 52

3. SAMPLE SIZE DETERMINATION

Patients will be randomly allocated in a 5:3 ratio to the PDS arm or the comparator arm.

The primary endpoint is the proportion of patients with a \geq 2-step improvement from baseline on the ETDRS-DRSS at Week 52.

A sample size of 160 patients randomized in a 5:3 ratio (n=100 in the PDS arm and n=60 in the comparator arm) will provide over 99% power to detect an absolute difference of 35% between arms in proportion of patients with a \geq 2-step improvement

on ETDRS-DRSS at Week 52 under the following assumptions, and to provide adequate data for assessment of key secondary endpoints:

- An achievement of a ≥ 2-step improvement on the ETDRS-DRSS at Week 52 in 15% of patients in the comparator arm (Eylea® U.S. Package Insert; Brown et al. 2021)
- Fisher's exact test
- A 4.96% two-sided type I error rate (after adjustment for planned interim data reviews conducted by the iDMC prior to analysis of the primary efficacy endpoint; see Section 1.2.2)
- A 15% dropout rate by Week 52.

In case the 15% dropout rate by Week 52 is deemed under-estimated during the study enrollment period, the sample size may be increased accordingly based on a revised dropout rate estimate. However, at the time of closing to recruitment, the dropout rate was approximately 5%. It was determined that the sample size did not need to be further increased.

Detailed information regarding the sample size assumptions and calculation is provided in Appendix 1.

4. ANALYSIS SETS

The following populations are defined:

Table 1 Analysis Sets

Population	Definition
ITT Population	All patients who are randomized. Patients will be grouped according to treatment assigned at randomization.
Safety-Evaluable Population	All patients who receive any study treatment, and patients randomized to the comparator arm under observation, grouped according to treatment actually received prior to Week 52. In the PDS arm, the population includes all patients randomized to PDS receiving at least one loading dose, or any patient who received the PDS implant prior to Week 52. In the comparator arm, the population includes all patients randomized to the comparator arm who did not receive the PDS implant prior to Week 52.
PDS Safety Population	All patients who receive the PDS implant, including patients in the comparator arm who cross over to receive PDS at Week 64. Analyses on this population will only include data after first loading dose. Patients will be grouped according to treatment actually received prior to Week 52 (i.e. patients receiving PDS prior to Week 52 are grouped to the PDS arm, and patients receiving PDS after Week 52 are grouped to the comparator arm).
PDS PK Population	All patients who are randomized with at least one post implant PK sample available and who receive PDS at any time point, grouped according to treatment actually received prior to Week 52, and overall. Analysis is relative to time since implant insertion.

PDS PK Evaluable Population	All patients in the PDS PK Population excluding patients receiving intravitreal injections of ranibizumab in the study eye post PDS implant (including supplemental treatment) or patients with fellow eye ranibizumab after randomization, or bevacizumab treatment in either eye within 9 months prior to randomization or after randomization, or patients with septum dislodgment. Patients will be grouped according to treatment actually received prior to Week 52, and overall. Analysis is relative to time since implant insertion.
Aqueous Humor PK Evaluable Population	Subset of patients in the PDS PK Evaluable Population with at least one post implant aqueous humor PK sample. Patients will be grouped according to treatment actually received prior to Week 52,and overall.
Aqueous Humor Biomarker Evaluable Population	All patients who are randomized and receive study treatment, including patients randomized to the comparator arm under observation, and have at least one optional aqueous humor sample available. Patients who receive the PDS implant insertion at any other times besides Week 4, 8, 64 or 68 will be excluded from this population. Patients who receive PDS implant insertion at Week 4 or 8 will be grouped in the PDS arm. Patients who receive PDS implant insertion at Week 64 or 68 will be grouped in the comparator arm.

ITT = intent-to-treat; PDS = Port Delivery System with ranibizumab; PK = pharmacokinetic

5. STATISTICAL ANALYSES

The primary analysis will be performed when all patients have completed the Week 52 follow up, or have discontinued from the study prior to Week 52, all data collected through Week 52 are in the database, and the data have been cleaned and verified.

Additional analyses may be performed to support the requirements of health authorities relative to marketing applications, as appropriate.

The final analysis will be performed when all patients have either completed the study (the end of which is determined at the Sponsor's discretion, depending on health authority approval of the PDS for the DR indication and Sponsor decision) or discontinued early from the study, all data from the study are in the database, and the database is locked.

Results from the primary analysis, summarized by treatment group, may be reported to the public before completion of the study.

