 - b) PDS patients who were ADA positive at the reference visit and ADA titer increased after implant; in this case, the titer results of one or more samples collected after implant are at least 0.60 titer units greater than the titer result of the reference visit sample. These patients are considered to have treatmentenhanced ADA responses.

The combined rates described in (a) and (b) above will provide the incidence of patients positive for treatment-emergent ADAs. Patients are considered to be negative for Treatment-emergent ADAs if they are ADA negative at all timepoints after the reference visit. Patients are also considered to be Treatment unaffected for ADAs if they are ADA positive at the reference visit and (a) where all post-baseline titer results are less than 0.60 t.u. greater than the titer result of the reference visit, OR (b) where all post-baseline results are negative or missing. A listing of patients with positive serum antibodies to ranibizumab will be provided.

The immunogenicity assessment will also include testing for the presence of neutralizing antibodies in samples confirmed to be positive for anti-ranibizumab antibodies. The incidence of neutralizing antibodies will be grouped and reported in a similar fashion to that described above.

The relationship between ADA status and safety, efficacy, PK, and biomarker endpoints may be explored.

5.7.5 Biomarker Analyses

Biomarker analyses will be performed on the Aqueous Humor Biomarker Evaluable Population at the time of the Final Analysis. No biomarker analyses are planned at the Primary Analysis. Descriptive summaries of aqueous humor free VEGF concentration (original and log-transformed) and change in concentration from baseline will be tabulated and plotted by visit and by treatment arm.

The mean change from baseline in Free-VEGF log concentrations in the PDS arm at week W28 will be presented with a 95% CI.

The difference in the mean change from baseline in Free-VEGF fold change at W28/W24 between PDS and comparator arms respectively will be presented with a 95% CI.

Data after PDS implant from patients in the Aqueous Humor PK Population in patients with at least one post-implant Aqueous Humor PK sample will be summarized descriptively by treatment arm and overall.

Sensitivity analysis may be performed with the population that excludes patients who receive supplemental treatment.

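### The aqueous humor biomarker set excludes and groups patients by implant timing, which for the comparator arm lies after the Week 24 sample being compared

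*SAP*

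**What the plan says.** SAP Section 4, Table 1 builds the Aqueous Humor Biomarker Evaluable Population in three steps.

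- **Entry.** Randomised and treated patients enter, "including patients randomized to the comparator arm under observation", provided they "have at least one optional aqueous humor sample available". No implant is required.
- **Exclusion.** "Patients who receive the PDS implant insertion at any other times besides Week 4, 8, 64 or 68 will be excluded from this population".
- **Grouping.** "Patients who receive PDS implant insertion at Week 4 or 8 will be grouped in the PDS arm", and "Patients who receive PDS implant insertion at Week 64 or 68 will be grouped in the comparator arm". No other grouping rule is given.

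Section 5.7.5 says how the set is used: "Biomarker analyses will be performed on the Aqueous Humor Biomarker Evaluable Population at the time of the Final Analysis". Among the analyses listed there is a between-arm contrast: "Free-VEGF fold change at W28/W24 between PDS and comparator arms respectively will be presented with a 95% CI". Week 28 applies to the PDS arm and Week 24 to the comparator arm. The one sensitivity analysis mentioned there is optional and concerns supplemental treatment, not implant timing.

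**The concern.** A comparison of arms at Week 24/28 should depend only on facts known by then. Here a comparator patient's place in the comparison can depend on surgery that happens long after the sample was taken. Because the biomarker analyses are run only at the final analysis, the later implant history will be known when the set is formed, so the rule will take effect.

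Two things are at stake. First, the comparator group at Week 24 may lose patients for a reason that arose after the measurement, so the contrast is no longer one of the groups as randomised. Second, the text leaves a programmer without a group for patients who never receive an implant. Dropping them or assigning them by improvisation are both possible, and the two choices can give different results. In a subset that depends on optional samples, a few patients can matter.

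**Working it through.** The SAP gives no count or effect size for this subset, so there is no stated figure to reproduce. The check sets the definition against its use.

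**1. Timing of the deciding event relative to the sample**

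- Comparator arm: 64 − 24 = 40 weeks and 68 − 24 = 44 weeks. The implant that fixes the group comes 40 to 44 weeks *after* the sample.
- PDS arm: 28 − 4 = 24 weeks and 28 − 8 = 20 weeks. The implant comes 20 to 24 weeks *before* the sample.

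The same rule therefore conditions on the past in one arm and on the future in the other.

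**2. Applying the three steps to each kind of patient with a usable baseline and on-visit sample**

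| Patient | In the set? | Stated group |
|---|---|---|
| Comparator, implant Week 64 or 68 | Yes | Comparator |
| Comparator, implant off schedule, e.g. Week 72 (72 − 24 = 48 weeks after the sample) | No | – |
| Comparator, leaves before Week 64 or is never implanted | Yes | None |
| PDS arm, implant Week 4 or 8 | Yes | PDS |
| PDS arm, implant off schedule, e.g. Week 12 (28 − 12 = 16 weeks before the sample) | No | – |
| PDS arm, loading doses only, never implanted | Yes | None |

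Row 2 is the certain case of exclusion by a later event. Rows 3 and 6 are a certain gap in the grouping. They become exclusions only if the two grouping sentences are read as exhaustive.

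**3. Comparison with the neighbouring sets**

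In the same table, the Safety-Evaluable Population groups by treatment received before Week 52 and expressly puts comparator patients not implanted by then in the comparator arm. The biomarker set has no such fallback.

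**4. Size, by assumption only**

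Let *f* be the share of comparator patients with a Week 24 sample who are left out, and *D* the difference, in SD units, between their mean and the mean of those kept. The full mean equals the kept mean + *f* × *D*, so leaving them out shifts the comparator mean by *f* × *D* in absolute size. Neither *f* nor *D* is in the SAP. The values below are assumed, and the higher shares presuppose that ungrouped patients are dropped as well.

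| Assumed *f* | Of about 60 comparator patients | Shift at *D* = 0.5 | Shift at *D* = 1.0 |
|---|---|---|---|
| 5% | 3 | 0.025 SD | 0.05 SD |
| 15% | 9 | 0.075 SD | 0.15 SD |
| 25% | 15 | 0.125 SD | 0.25 SD |

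The middle column refers to the whole arm. The number with an optional sample is not given and would be smaller.

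**The case against.** The strongest defence is that the set is wider than the grouping sentences suggest. A comparator patient under observation enters on a sample alone. The exclusion reaches only patients who *do* receive an implant at another time. Anyone who drops out or is never implanted stays in, and a sensible programmer would use the randomised arm for them. Off-schedule implants should also be rare: Section 1.2 allows one postponement of about 4 weeks, and 4 + 4 = 8 and 64 + 4 = 68 are already on the permitted list. Finally, the biomarker objectives are exploratory (Section 1.1.5), and the contrast is an estimate with an interval, outside the fixed testing sequence of Section 2.1.

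Most of this stands, and it rules out some stronger readings.

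- A reader might infer that an implant at Week 64 or 68 is a condition of entry for comparator patients. The entry sentence says otherwise.
- A reader might apply the dropout figures in Section 3 (15% planned by Week 52, about 5% at close of recruitment) to estimate the loss. Those rates are trial-wide, do not describe comparator patients between Week 24 and Week 64, and count people whom the definition does not exclude.
- A reader might suppose that the patients lost are those with rising VEGF, so that the comparator is selected for a good course. Nothing in the SAP shows this. Progression is not an exclusion criterion for this set, and Section 1.2 ties postponement to extenuating circumstances, which may be logistical.
- A reader might suppose that the PDS arm is untouched. It is not: off-schedule implants are excluded there too, and the never-implanted have no group.

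What the defence does not answer is the off-schedule comparator implant, which the exclusion sentence removes plainly, and the absence of any written group for never-implanted patients.

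**Conclusion.** The point holds in a limited form. Followed as written, the definition removes a comparator patient with valid baseline and Week 24 samples because of an off-schedule implant placed after that sample. It also leaves never-implanted patients of both arms in the set without a group. Whether those patients are dropped depends on how the grouping sentences are read, and the SAP does not settle this.

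The number affected is unknown and may be small. The direction of any bias is unknown. The shifts worked out above illustrate scale under assumed inputs and do not estimate what will happen. No primary, key secondary or safety result is touched. Severity is low. The reason to act is that the correction is specific and nearly free.

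**What to change.** Amend Table 1 and Section 5.7.5 as follows.

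- For biomarker summaries and comparisons at or before Week 60, include every randomised patient with a baseline and an on-visit aqueous humor sample.
- Group these patients as randomised, and say expressly that this covers patients never implanted, in both arms.
- Do not use implant timing after the sample to exclude or group anyone.
- State how a comparator patient implanted before the sample is handled.
- Keep the Week 4, 8, 64 or 68 rule for post-implant summaries, where implant timing is relevant.

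The cost is a few lines of SAP text and one change to the derivation of the set and its grouping variable. No new data are needed. Since the biomarker analyses are planned only for the final analysis, the change does not affect the planned primary analysis.

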5.1 GENERAL CONSIDERATION

Efficacy analyses will be based on the intent-to-treat (ITT) Population unless otherwise specified.

Descriptive summaries will include the mean, standard deviation (SD), median, and range for continuous variables, and counts and percentages for categorical variables. Missing data for descriptive summaries will not be imputed unless otherwise noted.

For all efficacy endpoints, comparative efficacy analyses will be performed during the comparator-controlled treatment period (randomization through Week 60). At the primary

analysis, only the efficacy assessments collected through Week 52 will be included in the comparative efficacy analyses and descriptive summaries. At the final (end of study) analysis only the efficacy assessments collected through Week 60 will be included in the comparative efficacy analyses and data collected through end of study will be included in summaries. For the safety summaries, only data reported through Week 52 will be included at the time of the primary analysis. At the time of the final analysis, safety summaries will include all safety data collected through end of study (see Section 5.6).

Unless otherwise noted, analyses of efficacy outcome measures will be stratified by the randomization stratification factors (ETDRS-DRSS level [47 vs. 53] and intraretinal or subretinal fluid status on SD-OCT [present vs. absent] as assessed at baseline by a central reading center) as recorded in IxRS.

A nominal type I error penalty of 0.0001 (two-sided) will be taken for each time the iDMC conducts an unmasked interim safety review prior to the primary analysis. At the time of the primary analysis, four interim data reviews have been conducted by the iDMC; therefore, efficacy analyses will be performed at a significance level of 0.0496. All CIs will be two-sided and at the 95.04% level.

The occurrence of each type of intercurrent event as defined in Section 5.3.1 will be summarized by treatment arm. Additionally, the occurrence of each type of intercurrent event due to coronavirus disease of 2019 (COVID-19) as defined in the supplementary analysis in Section 5.3.3 will be summarized by treatment arm.

Data collected in selected scheduled and unscheduled visits will be mapped to visits that appear in the schedule of assessments (see Appendix 1 of the Protocol) per the Protocol using the actual study day of assessment.

If there are multiple values in the same visit window, values closest to the scheduled study day will be used in the analysis. In the case of a tie, the worst-case value will be used. The value to be used in the analysis will be selected prior to the implementation of intercurrent event strategies. For patients in the ITT Population, the day of randomization will be designated Study Day 1. For the other populations, Day 1 is defined as the day that study treatment was first received (or day of randomization for comparator patients not receiving study treatment). Each assessment will be assigned a study day calculated as:

date of assessment - date of randomization or first study treatment +1

Baseline in the ITT Population is defined as the last non-missing value at or prior to Day 1. Typically, baseline will be the pre-dose Day 1 assessments, but may include screening results if the pre-dose Day 1 result is not available or missing, or if it is not collected at Day 1 according to the schedule of assessments.

In order to avoid potential confounding of the effect of explant procedure on efficacy analyses, for all efficacy summary tables analyses will include baseline data and all post-baseline data except for efficacy data collected within 37 days following explant procedure. In the case of an explant and re-implant occurring on the same day, efficacy data collected within 37 days following the explant and re-implant procedure will be excluded from all efficacy summary tables because of the expected temporary impact in the immediate post-operative period on these outcomes. These post explant exclusions of efficacy data will not apply to efficacy listings. Non-standard BCVA data (assessed by ETDRS BCVA testing with prior visit refraction, test performed by unmasked certified ETDRS BCVA assessor, or by uncertified experienced ETDRS BCVA assessor) will be excluded from the analysis and provided in a separate listing. ETDRS-DRSS scores of 90 represent that the image was not able to be graded so will be treated as missing and provided separately in a listing.

5.2 PATIENT DISPOSITION

Patient disposition (the number of patients randomized, treated, and completing the comparator-controlled treatment period ending at Week 52 (at the primary analysis) and at Week 60 (at the final analysis) and over the entire study) will be tabulated by treatment group in the ITT Population. Reasons for premature study treatment discontinuation and study discontinuation will be tabulated and a listing will be provided. Detailed, free text reasons for discontinuations due to physician decision, withdrawal by subject and 'other' reasons will be included in the listing.

5.3 PRIMARY EFFICACY ENDPOINT ANALYSIS

5.3.1 Definition of Primary Endpoint

The primary efficacy endpoint is the proportion of patients with a \geq 2-step improvement from baseline on the ETDRS-DRSS at Week 52, where DRSS is assessed by a masked central reading center. The primary estimand is defined as follows:

- Population: Adult patients with moderately severe or severe NPDR (ETDRS-DRSS level 47 or 53) and no presence of CI-DME who are naive to any treatment for DR in the study eye
- Variable: $A \ge 2$ -step improvement from baseline on the ETDRS-DRSS at Week 52
- Intercurrent events which occur prior to Week 52:
 - a) Receiving any supplemental treatment: A composite variable strategy will be applied. Patients with this intercurrent event will be regarded as non-responders (i.e., they are regarded as not achieving 2-step improvement on the EDTRS-DRSS).
 - b) Receiving any prohibited therapy (as defined in Section 4.4.2 of the Protocol, including prohibited therapy administered post study treatment discontinuation), or PRP in the study eye: A composite variable strategy will be applied where patients with this intercurrent event will be regarded as non-responders.

- c) Discontinuing study treatment (PDS arm) or discontinuing study (comparator arm) due to an AE: A treatment policy strategy will be applied where all observed values will be used regardless of the occurrence of the intercurrent event.
- d) Discontinuing study treatment (PDS arm) or discontinuing study (comparator arm) due to lack of efficacy per Investigator's judgment: A treatment policy strategy will be applied where all observed values will be used regardless of the occurrence of the intercurrent event.
- Population-level summary: Difference in adjusted proportion between PDS and comparator arms as assigned at randomization.

5.3.2 Main Analytical Approach for Primary Endpoint

The primary analysis will be performed using the Cochran–Mantel–Haenszel (CMH) test stratified by baseline ETDRS-DRSS level (47 vs. 53) and intraretinal or subretinal fluid status on SD-OCT (present vs. absent) as assessed at baseline by a central reading center and as recorded in IxRS.

Patients receiving supplemental treatments, prohibited therapy, or PRP (intercurrent events a-b) may experience an improvement in the ETDRS-DRSS level as a result which would potentially bias the results in favor of an ineffective treatment. Their ETDRS-DRSS level at Week 52 will be imputed using the assumption that they did not have a \geq 2-step improvement from baseline.

ETDRS-DRSS level for patients who discontinue study treatment due to lack of efficacy or AE are unlikely to change in the absence of supplemental treatments, prohibited therapy or PRP and inclusion of data following treatment discontinuation is unlikely to bias results. Therefore, their assessments after the intercurrent events c-d (but before receiving supplemental treatment or prohibited therapy or PRP) will be included in the analyses. For these patients who discontinue study treatment due to lack of efficacy or AE who are also missing ETDRS-DRSS level at Week 52 the last observed ETDRS-DRSS level prior to Week 52 will be imputed.

If there are no post-baseline ETDRS-DRSS levels observed, the baseline level will be imputed (patient regarded as non-responder).

If a patient has more than one intercurrent event, the composite strategy in which patients are included as non-responders will take precedence over the treatment policy strategy.

For patients who do not have intercurrent events a-d and are missing ETDRS-DRSS level (including death) at Week 52, the outcome at Week 52 will be imputed using the last observed outcome prior to Week 52. Patients with missing baseline outcomes will be excluded from the analysis.

The proportion of patients in each treatment group and the overall difference in proportions between treatment groups will be estimated using the weighted average of the observed proportions and the differences in observed proportions over the strata defined by randomization stratification factors of baseline ETDRS-DRSS and baseline intraretinal or subretinal fluid status using the CMH weights (Cochran 1954; Mantel and Haenszel 1959) as recorded in IxRS. CIs of the difference in proportions between treatment groups will be calculated using the normal approximation to the weighted proportions (Mehrotra and Railkar 2000).

5.3.3 Supplementary Analyses for Primary Endpoint

A supplementary analysis will be performed in which patients experiencing any intercurrent event prior to Week 52 will be regarded as a non-responder (i.e., they are regarded as not achieving 2-step improvement on the EDTRS-DRSS). The analysis method and the missing data handling rule for this supplementary analysis will be the same as those for the main analysis. The supplementary analysis will represent a conservative non-responder imputation strategy, which regards need for supplemental treatment, prohibited therapy, or PRP, or treatment discontinuation due to AE or lack of efficacy as a treatment failure regardless of their observed outcome at Week 52.

In the main analysis, after applying the intercurrent event strategies, missing data are imputed using the last observed ETDRS-DRSS level. In order to assess the impact of this imputation method, a supplementary analysis will be performed in which no missing data imputation is applied after the intercurrent event strategies have been implemented (completer analysis).

In order to estimate the treatment effect in the absence of the COVID-19 pandemic, a supplementary analysis will be performed using the same elements of the estimand as those in the main analysis, but including additional intercurrent events related to COVID-19. For these COVID-19 related intercurrent events (e-h) the hypothetical strategy of censoring observations after the intercurrent event is used. Missing data are then imputed using the last observed outcome prior to the intercurrent event.

- Intercurrent events which occur prior to Week 52:
 - a) Receiving any supplemental treatment: A composite variable strategy will be applied where patients will be regarded as non-responders (i.e., they are regarded as not achieving 2-step improvement on the EDTRS-DRSS).
 - b) Receiving any prohibited therapy (as defined in Section 4.4.2 of the Protocol, including prohibited therapy administered post study treatment discontinuation) or PRP in the study eye not due to COVID-19: A composite variable strategy will be applied where patients will be regarded as non-responders.
 - c) Discontinuing study treatment (PDS arm) or discontinuing study (comparator arm) due to an AE not due to COVID-19: A treatment policy strategy will be applied where all observed values will be used regardless of the occurrence of the intercurrent event.

- d) Discontinuing study treatment (PDS arm) or discontinuing study (comparator arm) due to lack of efficacy per Investigator's judgment not due to COVID-19: A treatment policy strategy will be applied where all observed values will be used regardless of the occurrence of the intercurrent event.
- e) Receiving any prohibited therapy (as defined in Section 4.4.2 of the Protocol, including prohibited therapy administered post study treatment discontinuation) or PRP in the study eye due to COVID-19: A hypothetical strategy will be applied where all values will be censored after the intercurrent event.
- f) Discontinuing study treatment (PDS arm) or discontinuing study (comparator arm) due to COVID-19: A hypothetical strategy will be applied where all values will be censored after the intercurrent event.
- g) Deviating from planned treatment administration schedule with potentially major impact on efficacy due to COVID-19: A hypothetical strategy will be applied where all values will be censored after the intercurrent event.
 - PDS Arm: Any missed implant or refill-exchange due to COVID-19, or missed 2 or more consecutive missed visits due to COVID-19 immediately followed by a supplemental treatment (reported as an intercurrent event at the second missed visit)
 - Comparator Arm: Two or more consecutive missed visits due to COVID-19 immediately followed by a supplemental treatment (reported as an intercurrent event at the second missed visit)
- h) Death related to COVID-19: A hypothetical strategy will be applied, patient will be censored at the time of death.

The analysis methods for this supplementary analysis will be the same as those for the main analysis. Missing ETDRS-DRSS at Week 52 will be imputed using the last observed outcome prior to Week 52. Patients with missing baseline outcomes will be excluded from the analysis.

